10.1 Disposition of Subjects and Discontinuations

This following will be presented in a summary table:

- Total number of subjects screened (ie, subjects who gave informed consent)
- Number of screened subjects who discontinued from the trial prior to treatment overall and grouped by the main reason for discontinuation:
 - Subject did not meet all eligibility criteria
 - Withdraw consent
 - Adverse event
 - Lost to follow-up
 - Death
 - Other
- Number of treated subjects by treatment and overall
- Number and percentage of treated subjects who completed study by treatment and overall

- Number and percentage of treated subjects who discontinued the study, with the primary reason of discontinuation by treatment and overall:
 - Adverse event
 - Lost to follow-up
 - Protocol non-compliance
 - Death
 - Withdrew consent
 - Other

A listing of discontinued subjects will be provided.

10.2 Protocol Deviations

10.2.1 Important Protocol Deviations

Listings of important protocol deviations will be provided including the date and relative day in relation to dosing in the relevant period.

10.2.2 Reasons Leading to the Exclusion from an Analysis Set

All criteria/reasons leading to the exclusion of a subject from an analysis set will be listed based on the safety set.

Reasons for excluding individual PK concentrations will also be listed separately and flagged in the main listing based on the safety analysis set.

11 Demographics and Other Baseline Characteristics

11.1 Demographics

Summaries will be given for both the safety and the pharmacokinetic set, if different.

Demographic characteristics will be listed by subject and summarized using the following information from the Screening/Baseline Visit eCRF pages.

Demographic characteristics:

- Sex: male, female
- Race: Black or African American, American Indian or Alaska Native, Asian, Native Hawaiian or Pacific Islander, White, Other

- Ethnic origin: Hispanic or Latino , Not Hispanic or Latino
- Age (years): summary statistics
- Height (cm) at Baseline: summary statistics
- Weight (kg) at Baseline: summary statistics
- BMI (kg/m²) at Baseline: summary statistics

Age will be taken from the eCRF and cannot be derived from the data because only the year of birth is collected in the eCRF.

BMI will be re-derived (ie, not taken directly from the database) according to the following formula:

- BMI (kg/m²) = weight (kg) / (height (m) * height (m))

11.2 Medical History

The medical history will be listed by subject including the preferred term and MedDRA system organ class (SOC) body using MedDRA, current version.

11.3 Other Baseline Characteristics

Other baseline characteristics will be listed by subject and summarized using the following information from the Screening/Baseline Visit eCRF pages.

Other baseline characteristics:

- Smoking status
- Alcohol consumption

12 Previous or Concomitant Medications/Procedures

Previous medications are medications, other than trial medications and pre-medications for trial drug, which started and stopped before first administration of trial drug.

Concomitant treatments are medications, other than trial medications, which are taken by subjects any time on-trial (on or after the first day of trial drug treatment for each subject).

In case the date values will not allow to unequivocally allocating a medication to previous or concomitant medication the medication will be considered as concomitant medication

Any previous and concomitant medication will be encoded with WHO-DD, latest version. Prior and concomitant medications will be listed by subject (all subjects).

The following information will be displayed in a listing: generic or trade name (as reported in CRF), WHO drug name (including ATC-2nd level and preferred term), dose/unit, route, frequency, reason for use, start/end date and time.

Concomitant procedures will be presented in a data listing.

13 Treatment Compliance and Exposure

A listing of date and time of each drug administration and each blood sampling including time deviations will be provided sorted by subject.

14 Efficacy Analyses

Not applicable.

15 Safety Analyses

The subsections in this section include specifications for summarizing safety endpoints that are common across clinical trials such as adverse events, laboratory tests and vital signs.

Safety data analysis will be conducted on the Safety Analysis Set.

15.1 Adverse Events

The number and percentage of subjects experiencing at least one TEAE will be summarized by treatment as well as the number of events. A TEAE is an AE with onset after start of treatment. Tables by relationship to trial drug and by severity will be generated. AEs will be coded using Medical Dictionary for Regulatory Activities terminology, latest version.

Incomplete TEAE-related dates will be handled as follows:

- In case the onset date is missing completely or missing partially but the onset month and year, or the onset year are equal to the start of trial treatment then the onset date will be replaced by the minimum of start of trial treatment and TEAE resolution date.
- In all other cases the missing onset day or missing onset month will be replaced by 1.

- Incomplete stop dates will be replaced by the last day of the month (if day is missing only), if not resulting in a date later than the date of subject's death. In the latter case, the date of death will be used to impute the incomplete stop date.
- In all other cases the incomplete stop date will not be imputed.

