Part A investigates the bioequivalence of TF3 and TF2 under fasted condition and is designed in 2 stages. If the PK-variability in Stage 1 is larger than initially assumed, the sample size will be re-calculated (with alpha-correction) and additional subjects may be randomized in Stage 2.

Parts B and C investigate the effect of food on the PK of tepotinib after administration of TF2 (Part B) and TF3 (Part C), respectively.

Each trial part has a 2-period, 2-sequence cross-over design. All 3 trial parts may be performed concurrently.

For each subject, the study consists of a screening period (Day -21 to Day -2) and 2 treatment periods, each lasting 21 days. Eligible subjects will be admitted to the clinical unit on Day -1. Subjects who continue to meet the eligibility criteria will be randomized to 1 treatment sequence on Day 1 of Period 1.

In each study period, the subjects will be hospitalized from Day -1 to Day 4 for safety assessments and PK blood sampling and return to the site on Days 5 - 8 for additional PK blood sampling and monitoring of AEs and concomitant medication. Study drug will be administered on Day 1 of each period. An End of Trial Visit will be performed at the end of Period 2 (21 days after dosing in Period 2).

Planned number of subjects:

At least 64 subjects; more subjects may be enrolled in accordance with the adaptive study design (Part A: 40 subjects in Stage 1, additional subjects in Stage 2, if required; Parts B and C: 12 subjects each).

Primary Endpoints:

- Part A: Area under the plasma concentration-time curve (AUC) from time zero (= dosing time) to the last sampling time at which the concentration is at or above the lower limit of quantification (AUC_{0-t}), AUC from time zero extrapolated to infinity ($AUC_{0-\infty}$) and maximum plasma concentration (C_{max}) of tepotinib observed from time zero to 168 h post-dose of each period
- Parts B and C: AUC_{0-t} , $AUC_{0-\infty}$ and C_{max} of tepotinib observed from time zero to 168 h post-dose of each period.

Secondary Endpoints:

- Time to reach C_{max} (t_{max}), terminal half-life ($t_{1/2}$), apparent total body clearance considering the fraction of dose absorbed (CL/f) and apparent volume of distribution during terminal phase (V_z/f) of tepotinib observed from time zero to 168 h post-dose of each period

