7.4.1.3 Definition of the Adverse Event Reporting Period

The AE reporting period for safety surveillance begins when the subject is initially included in the trial (date of first signature of informed consent) and continues until the End of Trial Visit.

Any SAE assessed as related to the IMP must be reported whenever it occurs, irrespective of the time elapsed since the last administration of the IMP.

7.4.1.4 Procedure for Reporting Serious Adverse Events, Adverse Events of Special Interest and Dose Limiting Toxicities

Serious Adverse Events

In the event of any new SAE occurring during the reporting period, the Investigator must immediately (within a maximum of **24 h** after becoming aware of the event) inform the Sponsor or its designee in writing. All written reports should be transmitted using the SAE Report Form, which must be completed by the Investigator following specific completion instructions.

In exceptional circumstances, an SAE (or follow-up information) may be reported by telephone; in these cases, a written report must be sent immediately thereafter by fax or e-mail. Names, addresses, and telephone and fax numbers for SAE reporting will be included in the trial-specific SAE Report Form.

Relevant pages from the eCRF may be provided in parallel (for example, medical history, concomitant drugs). Additional documents may be provided by the Investigator, if available (for example, laboratory results, hospital report, autopsy report). In all cases, the information provided on the SAE Report Form must be consistent with the data about the event recorded in the eCRF.

The Investigator must respond to any request for follow-up information (for example, additional information, outcome, final evaluation, other records where needed) or to any question the Sponsor/designee may have on the AE within the same timelines as those noted above for initial reports. This is necessary to ensure prompt assessment of the event by the Sponsor or designee and (as applicable) to allow the Sponsor to meet strict regulatory timelines associated with expedited safety reporting obligations.

Requests for follow-up will usually be made via the responsible Monitor, although in exceptional circumstances the Global Drug Safety department may contact the Investigator directly to obtain further information or to discuss the event.

Adverse Events of Special Interest

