7.4.4.2 Physical Examination

A standard examination will be performed including general appearance, skin, head, neck (including thyroid), eyes, ears, nose, throat, abdomen, as well as neurological, peripheral vascular, musculoskeletal, cardiovascular and pulmonary system.

Physical examination will be scheduled according to the Schedule of Assessments (see Table 1). Further physical examinations during the trial are at the discretion of the Investigator. Any relevant findings are to be recorded on the Medical History form in the eCRF (for findings from the past that occurred prior to ICF signature) or on the AE form in the eCRF (for findings presently occurring; events existing but unresolved prior to drug administration).

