8.2 Definition of Analysis Sets

Part A (Bioequivalence)

The PK Analysis Set for Part A will include all subjects without any relevant protocol deviations with respect to PK and absence of factors likely to affect the comparability of PK results, with adequate trial medication compliance, and who have valid primary endpoints for both treatments.

All PK analyses for Part A will be based on this analysis set.

Parts B and C (Food Effect)

The PK Analysis Set for each Part B and C, will include all subjects without any relevant protocol deviations with respect to PK and absence of factors likely to affect the comparability of PK results, with adequate trial medication compliance, and who have at least 3 post-dose concentration measurements.

All PK analyses for Parts B and C will be based on the respective PK analysis set.

All Parts (Safety)

The Safety Analysis Set will include all subjects who have received at least 1 dose of planned IMP in the respective Parts. Subjects will be analyzed according to the actual treatment they receive.

The screening analysis set will include all subjects who provided signed informed consent, regardless of treatment status in the trial. This set will be used for subject disposition.

For all Parts (A, B and C)

Subjects in a particular period may be excluded after vomiting or with diarrhea as this could render the plasma concentration-time profile unreliable. The use of a concomitant medication that might interfere with the PK of any investigational drug could be a reason for excluding a subject.

Relevant decisions will be made before database lock.

9 General Specifications for Data Analyses

Statistical analyses will be performed using the computer program package SAS® System for Windows™ (Version 9.4 or later; SAS Institute, Cary, North Carolina, USA).

The results of this trial will be reported using summary tables, figures, and data listings, as appropriate. All data will be summarized by treatment and/or scheduled time point, as appropriate.

This study has three separate parts (A, B and C). Outputs applicable to more than one part will be paged by part with the part indicated in a sub-heading.

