For demographic, baseline and safety assessments, continuous measurements will be summarized by means of descriptive statistics (ie, number and percentage of observations, number and percentage of missing observations, mean, standard deviation [SD], median, the first and third quartile [Q1 and Q3], minimum [Min], and maximum [Max]) and categorical data will be summarized by means of frequency tables (ie, count and percentages), if not stated otherwise. Mean, Median, Q1, Q3, Min, Max will have the same precision as the SDTM data (decimal places). SD will be presented with one decimal place more than the mean. For subject disposition and demographic tables the denominator will be the number of subjects in the analysis set. Counts of missing observations will be included as a separate category.

If not otherwise specified, „baseline“ refers to the last scheduled measurement before administration of the first drug in each period.

However, if a subject is missing the baseline collection, the previous non-missing evaluation could become the baseline value (e.g. from screening/admission). If no baseline or previous to baseline evaluations exist then the baseline value will be treated as missing.

The following calculations and derivations, as applicable, will be used:

- Change from baseline: post-baseline visit value - baseline value
- Duration of AE (in days hh:mm) = end date and time - start date and time of the AE, if missing time for either the beginning or end then = end date – start date + 1
- Days hh:mm from dosing = start date and time of the event - date and time dose administration; (for treatment-emergent AEs), if missing time for either the dosing or event then = event start date – date of dose administration + 1
- Rel. Day in period of AE = start date of the event – date of First Admin in period + 1 (for AEs on or after the day of dosing)
- Rel. Day in study of AE = start date of the event – date of First Admin (for AEs before the day of dosing of the study only)

Repeated laboratory assessments will be flagged as repeats in the subject data listings and not included in summary tables statistics (unless the scheduled measurement was considered unreliable, e.g. due to technical reasons, and needed to be replaced by an unscheduled repeat measurement).

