15.1.1 All Adverse Events

All AEs recorded during the course of the trial (ie, assessed from signature of informed consent until the end of the Follow-up/End of Trial visit) will be coded according to MedDRA latest version and assigned to a SOC and PT.

TEAEs will be summarized by severity, using MedDRA latest version preferred term as event category and MedDRA primary system organ class (SOC) body term as Body System category. The severity of AEs will be graded using the “National Cancer Institute - Common Terminology Criteria for Adverse Events” (NCI-CTCAE) guideline, version 5.0 (publication date: 27 Nov 2017), as detailed in the study protocol.

TEAEs related to trial treatment are those events with relationship missing, unknown or related.

The following will be summarized in an overview table with the number and percentage of subjects (and the number of events) by treatment and overall:

- Any TEAEs
- Any trial treatment related TEAEs
- Any serious TEAEs
- Any trial treatment related serious TEAEs
- Any TEAE (grade ≥ 3)
- Any trial treatment related TEAEs (grade ≥ 3)
- Any TEAEs leading to death
- Any trial treatment related TEAEs leading to death

TEAEs will be summarized by treatment and overall in tables with:

- The number and percentage of subjects by treatment with at least one TEAE and the number of events overall and by SOC and PT. Group/SOC terms will be sorted alphabetically and PTs within each group/SOC term will be sorted by descending frequency.
- The number and percentage of subjects by treatment with at least one non-serious TEAE and the number of non-serious TEAE applying frequency threshold of 5%. Group/SOC terms will be sorted alphabetically and PTs within each group/SOC term will be sorted by descending frequency.

In addition the following tables will be provided. Group/SOC terms will be sorted alphabetically and PTs within each group/SOC term will be sorted by descending frequency (based on all treatment groups combined):

- A table by severity of TEAEs with the number and percentage of subjects by treatment with at least one TEAE and the number of events by SOC and PT.
- A table by relationship to trial treatment with the number and percentage of subjects by treatment with at least one TEAE and the number of events by SOC and PT.

Pre-treatment AEs (AEs with onset after informed consent but before start of treatment) and TEAEs will be listed separately.

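### The SAP defines a TEAE by onset alone, with no provision for worsening after dosing and no rule assigning an AE to one of the two crossover treatments

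*SAP*

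**What the plan says.** SAP 15.1 states: "A TEAE is an AE with onset after start of treatment". The protocol uses TEAEs as a secondary endpoint (8.4.2) but does not define the term. SAP 15.1.1 applies the same split by onset: "Pre-treatment AEs (AEs with onset after informed consent but before start of treatment) and TEAEs will be listed separately".

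Events with onset before dosing do reach the AE data. Protocol 7.4.1.3 opens the reporting period at consent, and screening can start on Day -21. Protocol 7.4.4.2 sends relevant examination findings to the AE form "for findings presently occurring; events existing but unresolved prior to drug administration".

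The outputs are by treatment. SAP 15.1: "The number and percentage of subjects experiencing at least one TEAE will be summarized by treatment as well as the number of events". The protocol synopsis describes the design: "Each trial part has a 2-period, 2-sequence cross-over design". On which treatment an event belongs to, the SAP offers only two pieces of text. Section 8.2, on the Safety Analysis Set, says "Subjects will be analyzed according to the actual treatment they receive". Section 9 has derivations that count from the event's start, such as "Rel. Day in period of AE = start date of the event" minus the date of first administration in the period, plus 1.

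**The concern.** A definition by onset alone can miss a drug effect that appears as the worsening of something already present. A Grade 1 complaint noted on Day -1 that becomes Grade 2 or 3 after dosing still has a pre-dose onset.

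The crossover adds a second question. When each subject takes two treatments and the tables are by treatment, every event needs an assignment rule. An event that starts after the first dose and worsens after the second bears on both treatments, and the SAP does not say where either the event or its higher grade is counted.

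What is at stake is the secondary safety endpoint: incidence, frequency, intensity and causality of TEAEs for TF3 against TF2 and for fed against fasted. The primary endpoints are pharmacokinetic and are untouched.

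**Working it through.** The plan states no figure to reproduce, so the check is to trace two cases through the text, each under the two possible ways of recording a worsening.

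| Case | Worsening kept in the original record | Worsening entered as a new AE |
|---|---|---|
| Onset between consent and first dose, worse after dosing | Pre-treatment AE: listed, in no TEAE table | New onset is post-dose, so it is a TEAE |
| Onset after the Period 1 dose, worse after the Period 2 dose | TEAE; treatment column not specified; start-date derivations point to Period 1 | New onset lies in Period 2 |

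**First case.** SAP 15.1 and 15.1.1 together classify a single record by its onset. The TEAE outputs that would then omit it are the overview table (including its Grade 3 or higher rows), the tables by SOC and PT, severity and relationship (15.1.1), and the table of TEAEs leading to discontinuation (15.1.2). The SAE table in 15.2.2 is not restricted to TEAEs.

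**Second case.** Analysing by actual treatment does not resolve it, because the subject actually received both. The section 9 derivations are the nearest guide. They give timing variables computed from the event's start and are not an assignment rule. They make Period 1 the natural reading, but they do not prescribe it.

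**Which column of the table applies.** Protocol 7.4.1.2 says that adverse changes in the subject's condition during the reporting period are to be entered as AEs. That can be read as opening a new record at worsening, but it does not clearly require one. The same section asks for onset and resolution dates and a severity for each event, does not ask for a date of grade change, and leaves detail to the eCRF Completion and Monitoring Conventions, a separate document.

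**Size of one event**, taking the planned numbers as the denominator for a treatment:

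- Part B or Part C, 12 subjects each: 1/12 = 0.083, or 8.3 percentage points.
- Part A Stage 1, 40 subjects: 1/40 = 0.025, or 2.5 percentage points.

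These are upper limits per event on a treatment's subject incidence. If the subject has another TEAE on the same treatment, the overall incidence does not change at all.

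**The case against.** The strongest reply is that the recording rule in Protocol 7.4.1.2 already deals with this. Read in the ordinary way, a post-dose worsening is an unfavourable change, gets its own AE with a post-dose onset, and is captured by the present definition. The conventions document may say so outright. This stands to the extent that both consequences are conditional. It does not remove the point, because the tables then depend on a recording convention that neither the protocol nor the SAP states.

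A second reply is that the route is narrow and partly covered elsewhere. Subjects must be healthy at Screening and on Day -1. In 79 earlier healthy subjects all TEAEs were mild to moderate apart from one Grade 3 lipase elevation. Grade 3 or higher lipase or amylase elevations are recorded and listed as AESIs. SAEs have their own table. Laboratory grade shifts from pre-dose to Day 4 are tabulated within period, and QTcF change from period baseline is categorised. All of this stands and limits the importance of the gap. It leaves uncovered a non-serious symptom that rises in grade after a dose. The SAE table is also by treatment, so it needs the missing assignment rule too.

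A reader might go further and infer that the SAP places a Period 2 worsening under Period 1 at its worst grade. It does not say so: it has neither an assignment rule nor a stated rule for placing the higher grade. A reader might also infer that the later treatment is understated in a way that favours one formulation or food state. Each part randomises 1:1 to the two sequences (Protocol 8.3), so each treatment comes second in about half the subjects. Misplacement between periods would blur the comparison, but no systematic direction is shown.

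**Conclusion.** The point holds in a limited form. The SAP defines TEAEs by onset only, makes no provision for worsening after dosing, and does not say how an AE is assigned to a treatment in the crossover. The loss of pre-dose events from the TEAE tables follows from stated rules, on the assumption that worsening stays in the original record. The placement of a Period 2 worsening under Period 1 rests on that assumption and on an inference from the start-date derivations.

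It would be wrong to conclude that worsening events are certain to be missing from the TEAE tables, since the documents do not settle how they are recorded. The number of such events cannot be derived, so the 8.3 and 2.5 points describe one hypothetical event and do not estimate an effect. This is a worthwhile clarification of descriptive secondary safety tables, with no bearing on the bioequivalence or food-effect conclusions.

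**What to change.** In SAP 15.1:

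- Define a TEAE as an AE with onset, or worsening in CTCAE grade, after the first dose.
- Assign it to the most recent dose taken before that onset or worsening, and use the same rule for the SAE table.
- State that an original record and its worsening record are not both counted as TEAEs under the same treatment. Otherwise the new clause could inflate event totals.

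In addition, confirm that the eCRF conventions record a post-dose grade increase as a new record with its own start date and time, and add that line if it is absent.

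The cost is a few sentences in the SAP and at most one line in the conventions. The downside is a few more AE records and slightly higher TEAE counts. Design, sample size and pharmacokinetic analyses do not change.

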5.1 Overall Trial Design and Plan

This is a Phase 1, single-dose, open-label, 3 parts trial (Parts A, B and C; see [Figure 1](#)). In each of the parts, a 2-way, 2-period, 2-sequence cross-over design will be conducted. Part A has 2 stages. The procedure will follow the method C described by Montague [4] and Potvin [5]. All 3 study parts are planned to be conducted concurrently.

Part A has a two-stage adaptive design (see section [8.2.1](#)). This design is chosen due to the residual risk with respect to the PK-variability of tepotinib in the fasted state.

Stage 1 will be sufficiently powered to show the bioequivalence of the new tablet formulation (TF3) and the tablet formulation used in clinical studies (TF2), based on an assumption for PK-variability in the fasted state as data is not available. The Stage 2 will be performed only, if after

Stage 1, the PK-variability turns out larger than initially assumed. For Stage 2, additional subjects will be randomized based on the newly estimated PK-variability.

More details are given in Section [8.2.1](#).

Parts B and C will investigate the effect of food on the PK of tepotinib using a 2-way, 2-period, 2-sequence cross-over design following administration of the previous tablet formulation (TF2, Part B) and administration of the new tablet formulation (TF3, Part C), in 12 healthy subjects each. Each subject will receive the tablet under fasted and fed conditions.

Common Visit Schedule

Trial procedures are the same for all periods in all parts except for the food intake on Day 1.

The washout period will be at least 21 days between Day 1 of each period (see [Figure 2](#)).

A screening period is implemented from Day -21 to Day -2.

Subjects will be admitted to the study site on Day -1 of each period and will be resident at the study site under medical supervision from Days -1 to 4. They must visit the site on the morning of Days 5 to 8 for further blood sampling.

Blood and urine samples will be collected for laboratory assessments (hematology, biochemistry, urinalysis), which will be performed at Screening, throughout the in-patient period of each treatment period and for the End of Trial Visit.

Serial blood samples for PK assessments will be collected for 168 h after tepotinib administration in all periods.

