The End of Trial Visit is planned 21 days (\pm 1 day) after tepotinib administration in the second period. An Early Termination Visit will be conducted for subjects who withdraw prematurely. The same assessments as for the End of Trial Visit will be conducted at the Early Termination Visit.

Figure 1 Overall Trial Design

[figure not shown]

Figure 2 Design of the Trial Parts

Procedure	Parts A, B and C - All Periods			
	-1	1	2 - 4	5 - 8
Tepotinib administration		↑		
PK blood sampling		↔		
Safety assessments ^a	↔			
AE monitoring	↔			
Hospitalization	↔			

AE = adverse event, PK = pharmacokinetics

The washout period will be at least 21 days between Day 1 of each period.

^a Safety assessments: Vital signs, 12-lead electrocardiogram, clinical laboratory during hospitalization.

A detailed schedule of study procedures and assessments is provided in [Table 1](#).

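### The imputation rule for incomplete adverse-event onset dates ignores period, so in this crossover it dates many Period 2 events before the Period 2 dose

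*SAP*

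**What the plan says.** SAP 15.1 has two branches for an incomplete onset date. If the date is completely missing, or its known month and year (or year alone) equal those of the start of trial treatment, it is "replaced by the minimum of start of trial treatment and TEAE resolution date". Otherwise: "In all other cases the missing onset day or missing onset month will be replaced by 1". Neither branch mentions the period or the second dose.

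The SAP does not define the start of trial treatment, but the adverse-event section treats the start of treatment as one boundary per subject. SAP 15.1 says "A TEAE is an AE with onset after start of treatment", and SAP 15.1.1 says "Pre-treatment AEs (AEs with onset after informed consent but before start of treatment) and TEAEs will be listed separately". Where the SAP means a period it says so: SAP section 9 calculates one relative day of an adverse event from the first administration in the period, and SAP 15.4 and 15.5 use a period baseline.

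On the design, the protocol synopsis states "Each trial part has a 2-period, 2-sequence cross-over design". Protocol 5.1 adds "The washout period will be at least 21 days between Day 1 of each period" and, for the second period, "The End of Trial Visit is planned 21 days" after dosing (plus or minus one day). SAP 15.1 and 15.1.1 tabulate TEAEs by treatment. SAP 8.2 says that subjects are analysed by actual treatment. Neither document says how an event with an imputed onset is tied to a period.

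**The concern.** Anchoring to the first dose suits a trial in which each subject receives one treatment: it keeps a doubtful event inside the treatment-emergent window. Here each subject receives two treatments, and the other period is always the other formulation (Part A) or the other food condition (Parts B and C). An onset pulled back across the Period 2 dose therefore lands in the interval belonging to the other treatment.

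The occurrence of TEAEs is a secondary endpoint (protocol 8.4.2), and the related objective covers both formulations under fasting and non-fasting conditions. With 12 subjects in each of Parts B and C, one subject counted under the wrong treatment can change an incidence by up to 1/12, about 8 percentage points.

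**Working it through.** The plan gives no figure on this point, so the check applies the rule directly to dates.

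**Inputs from the documents.** Two doses per subject, D1 and D2, at least 21 days apart (21 used, 28 as a check); follow-up to about 21 days after D2; planned trial period Q3 to Q4 2018 (protocol synopsis).

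**Assumptions.** The start of trial treatment is D1. A Period 2 event resolves after D2, so the minimum of D1 and the resolution date is D1.

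**Onset wholly missing, or only the year known.** All dates in the planned trial period fall in 2018, so the first branch applies and the imputed onset is D1. This holds for 100% of Period 2 events.

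**Only the day missing.**
- If the onset month is the month of D1, the imputed onset is D1.
- Otherwise it is day 1 of the onset month.

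A Period 2 event is therefore dated before D2 whenever its onset falls in the same calendar month as D2, unless D2 is itself the first of the month. It stays in Period 2 if onset falls in a later month.

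*Start dates over a full year, 21-day gap:*

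| Onset, days after D2 | Cases | Imputed to D1 | Imputed to day 1, before D2 | Share before D2 |
|---|---|---|---|---|
| 0 to 21 | 365 × 22 = 8,030 | 593 | 4,401 | 4,994/8,030 = 62.2% |
| 8 to 21 | 365 × 14 = 5,110 | 25 | 2,481 | 2,506/5,110 = 49.0% |

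*Start dates limited to 1 July 2018 onward with the End of Trial Visit by 31 December 2018:* 84% for onset on Days 1 to 8 and 63% for Days 1 to 21. With a 28-day gap these become 84% and 65%.

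**Period 1 events.** The imputed date is either D1 or the first of a later month that is no later than the true onset, hence before D2. None moves to Period 2: 0% in every scenario.

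**Examples, day missing.**
- Doses 3 and 24 September, onset 26 September: imputed to 3 September. The Period 2 relative day by the SAP section 9 formula is 3 − 24 + 1 = −20; the true value is 26 − 24 + 1 = 3.
- Doses 17 September and 8 October, onset 10 October: imputed to 1 October. Relative day 1 − 8 + 1 = −6; the true value is 3.
- Doses 3 and 24 September, onset 4 October: imputed to 1 October, which stays in Period 2.

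**From date to treatment.** If an event is attributed to the last dose on or before its imputed onset, every event dated before D2 is counted under the other treatment. If it is attributed by recorded period, the tables stand, but the imputed date, the time from dosing and the relative day contradict that period, as in the first two examples.

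**The case against.** The strongest reply is that the step from date to treatment is inferred. No text says that TEAEs are allocated by comparing imputed onset with dosing dates, and SAP section 9 already handles adverse events by period. A reader might infer that the SAP assigns Period 2 events to the wrong treatment; the documents do not go that far. This stands, and it is why the wrong count is stated only conditionally. It does not rescue the rule, because under attribution by recorded period the imputed dates are still wrong.

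A second reply is that the start of trial treatment is undefined and could mean the start of the current period's treatment, in which case Period 2 events would stay in place. That is possible but less natural, given the single boundary between pre-treatment events and TEAEs and the explicit period wording elsewhere.

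Third, incomplete dates should be rare. Subjects are resident to Day 4 and seen daily on Days 5 to 8 (protocol 7.1.2), are asked about changes at each visit, with onset times to be recorded where timing relative to dosing matters (protocol 7.4.1.2), and queries are settled before database lock (SAP 6.2). This stands. What remains is mainly the interval after Day 8, when no visit is scheduled until the next admission or the End of Trial Visit. For that interval 49% is the more relevant share.

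Finally, the safety analysis is descriptive. With 1:1 sequences any shift exchanges treatments in both directions, so it blurs differences. A reader might infer bias towards TF3 or TF2, or doubt about bioequivalence; neither follows.

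**Conclusion.** The rule is wrong for this design, not merely short of detail: it exists only for incomplete dates, and on its most natural reading it places many Period 2 onsets before the dose they followed. The share is 100% when the onset date is wholly missing or only the year is known. With only the day missing it is about 62%, or about 49% for onsets 8 to 21 days after dosing, and the error runs in one direction by period. The day-missing figures rest on a 21-day gap, start dates uniform over a year and onset uniform over the stated days.

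These are shares of incompletely dated Period 2 events, not effects on the safety results. The documents give no rate of incomplete dates, and it is probably low. Counting under the other treatment follows only if attribution uses the imputed onset. The consequence is limited to some blurring, or internal contradiction, in a descriptive secondary summary. Severity: minor.

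**What to change.** In SAP 15.1:

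- State that a TEAE is assigned to the treatment of the period in which it is recorded as having started.
- Impute an incomplete onset to that period's dosing date, or to the earliest date consistent with the known date parts and the resolution date, but not before that period's dose.
- Where the period cannot be established after query, decide the assignment at the data review meeting and flag the event in the listing.

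If the recorded period is correct, no event in either period changes treatment. Two simpler anchors do not work. Using the latest dose in the known month keeps Period 2 events in place but moves 44% (onset Days 1 to 8) to 64% (Days 1 to 21) of Period 1 events with a missing day into Period 2. Using the latest dose before the reporting visit moves any Period 1 event first reported after the second dose.

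The cost is a sentence or two in the SAP and a small programming change, provided that the case report form identifies the period of onset; the documents do not show whether it does.
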